Plasma PK Sampling			X	X	X (Day 3, 11 and 13)	X	X	X	X	X	2mL of blood will be collected at pre-dose (within 15 mins prior to dosing) and 1, 2, 3, 4, 5, 6, 7, 8, 9, 10, 12, 16 and 24h post

Procedure	Pre-Treatment Days		Treatment Days			In House Post Treatment Days					Notes
	-2	-1	1	2, 4, 6, 8, 10, 12, 14	3, 5, 7, 9, 11, 13	15 (24 h)	16 (48 h)	17 (72 h)	18 (96 h)	19 (120 h)	
											dosing on Day 1 and Day 14. The 24 hour post Day 1 dose collection will be pre-dose on Day 2, the 24 hour post Day 14 dose collection will be post dose on Day 15 (24 hours after the last dose). Samples will also be collected pre-dose on Days, 3, 4, 6, 8, 10, 11, 12, 13 and once each day on days 16 (48 hours post last dose), 17 (72 hours post last dose), 18 (96 hours post last dose) and 19 (120 hours post last dose). PK sampling timepoints may be reduced. For further detail, see Section 8.4
Plasma Metabolite Sampling		X		X (Day 2 and Day 14)		X					Additional 2mL of blood will be collected at pre-dose (within 15 mins prior to dosing) and at the same timepoints as Plasma PK samples on Days 1, 2, 14 and 15 (as described above). For further detail, see Section 8.4
Urine PK and Metabolite Sampling		X		X (Day 2 end of 24 h collection from Day 1 and on Day 14)		X (end of 24 h collection from Day 14)	X	X	X	X	Collections at pre-dose (20 mL) (within 1 h prior to dosing) and from time 0 up to 24 h post dosing on Day 1 and from time 0 to 24h post dosing on Day 14. Spot urine sample collection on Day 16, 17, 18, and 19 at the post dose timepoint utilized on

Procedure	Pre-Treatment Days		Treatment Days			In House Post Treatment Days					Notes
	-2	-1	1	2, 4, 6, 8, 10, 12, 14	3, 5, 7, 9, 11, 13	15 (24 h)	16 (48 h)	17 (72 h)	18 (96 h)	19 (120 h)	
											Hours (h) relate to PK sampling post last dose
SAE Review											Day 1. For further detail, see Section 8.4
AE Review											All AEs will be collected from first dose until follow up visit
Concomitant Medication Review											

Table 3 continued Part 2 MAD Cohorts 3 and 4 – Outpatient Visit

Procedure	Day			Notes Hours (h) relate to PK sampling post last dose
	22 (192 h)	25 (264 h)	29 (360 h)	
Outpatient Visit	X	X	X	
Brief Physical Exam	X	X	X	Brief physical examinations may be made full and laboratory procedures may be repeated if needed at the discretion of the PI.
Vital signs	X	X	X	For further detail, see Section 8.1.2
12-lead safety ECGs	X	X	X	For further detail, see Section 8.1.4

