Testing for SARS CoV-2	X			X (Day 14)	X (Day 7)					X	An additional SARS-CoV-2 test will be performed approximately one week prior to admission to the unit. Weekly SARS-CoV-2 testing is required while in the unit (Days 7, 14) and on discharge (Day 23). An approved molecular test (PCR) will be used. For further detail see Appendix 7 and Section 8.1.3
Drug/alcohol/cotinine screen	X										
Haematology/Chemistry/Urine tests		X	X	X	X (Day 15)		X		X	X	For further detail, see Appendix 2
Pregnancy Test	X									X	Female participants only. For further detail see Appendix 2
VH3739937 Dose Administration			X	X	X						Once-daily oral dose from Day 1 to Day 18. Randomization to occur on Day 1 prior to dosing. For meal instructions prior to dose, see Section 5.3.1
Meals	Per site usual practice										
Plasma PK Sampling			X	X	X (Days 3, 15, 17)	X	X	X	X	X	2mL of blood will be collected pre-dose (within 15 mins prior to dosing) and 1, 2, 3, 4, 5, 6, 7, 8, 9, 10, 12, 16 and 24h post dosing on Days 1, 14 and Day 18. The

Procedure	Pre-Treatment Days		Treatment Days			In House Post Treatment Days					Notes
	-2	-1	1	2, 4, 6, 8, 10, 12, 14, 16, 18	3, 5, 7, 9, 11, 13, 15, 17	19 (24 h)	20 (48 h)	21 (72 h)	22 (96 h)	23 (120 h)	
											Hours (h) relate to PK sampling post last dose
											24 hour post Day 1 dose collection will be pre-dose on Day 2, the 24 hour post Day 14 dose collection will be post-dose on Day 15 and the 24 hour post Day 18 dose will be post dose on Day 19 (24 hours after the last dose). At all other timepoints on dosing days, samples will be drawn pre-dose prior to dose administration. On post dosing Days 20, 21, 22 and 23 samples will be collected at the same time of the day as the post-dose collections on dosing days. PK sampling timepoints may be reduced. For further detail, see Section 8.4
Plasma Metabolite Sampling		X		X (Days 2, 14 and 18)	X (Day 15)	X					Additional 2mL of blood will be collected pre-dose (within 15 mins prior to dosing) and at the same timepoints as Plasma PK samples on Days 1, 2, 14, 15, 18 and 19 (as described above). For further detail, see Section 8.4
Urine PK and Metabolite Sampling		X		X (Day 2 end of 24 h collection from Days 1, 14 and Day 18)	X (Day 15 end of 24 h collection from Day 14)	X (Day 19 end of 24 h collection	X	X	X	X	Collections at pre-dose (40 mL) (within 1 h prior to dosing) and from time 0 up to 24 h post dosing on Days 1, 14 and 18. Spot urine sample collection on

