Vital signs		X	X	X (Days 2, 4, and 6)	X	X (Days 10, 12 and 14)	X	X		X		X		Vital signs to be performed pre-dose. Temperature will be monitored every day during study participation. For further detail, see Section 8.1.2
12-lead safety ECGs		X	X	X	X	X	X	X	X	X	X	X		ECG should be performed pre-dose on dosing days. ECG timepoints may be reduced in subsequent dosing groups. For further detail, see Section 8.1.4
Testing for SARS CoV-2	X			X (Day 7)		X (Day 14)						X		An additional SARS-CoV-2 test will be performed approximately one week prior to admission to the unit. Weekly SARS-CoV-2 testing is required while in the unit (Days 7, 14) and on discharge (Day 20). An approved molecular

Procedure	Pre-Treatment Days		Week 1		Week 2		Week 3		In House Post Treatment Days					Notes
	Treatment Days		Treatment Days		Treatment Days									
	-2	-1	1	2, 3, 4, 5, 6, 7	8	9, 10, 11, 12, 13, 14	15	16 24h	17 48h	18 72h	19 96h	20 120h		
														Hours (h) relate to PK sampling post last dose
Drug/alcohol/nicotine screen	X													test (PCR) will be used. For further detail see Appendix 7 and Section 8.1.3
Haematology/Chemistry/Urine tests		X	X	X (Days 2, 4 and 6)	X	X (Days 9, 11 and 13)	X		X		X	X		For further detail, see Appendix 2
Pregnancy Test	X													Female participants only. For further detail see Appendix 2
VH3739937 Dose Administration			X		X		X							Weekly oral dose on Days 1, 8 and 15. Randomization to occur on Day 1 prior to dosing. For meal instructions prior to dose, see Section 5.3.1
Meals	Per site usual practice													
Plasma PK Sampling			X	X	X	X	X	X	X	X	X	X		2mL of blood will be collected at pre-dose (within 15 mins prior to dosing) and 1, 2, 3, 4, 5, 6, 7, 8, 9, 10, 12, and 16 h on Days 1, 8 and Day 15. The 24 h post day 1 dose collection on Days 2, 9 and 15 will be taken at post-dose collection timepoint. At all other timepoints on non-dosing days (Days 3, 4, 5, 6, 7, 10, 11, 12, 13, 14, 16, 17, 18, 19, 20), samples will be drawn at the post-dose

Procedure	Pre-Treatment Days		Week 1		Week 2		Week 3		In House Post Treatment Days					Notes		
	Treatment Days		Treatment Days		Treatment Days											
	-2	-1	1	2, 3, 4, 5, 6, 7	8	9, 10, 11, 12, 13, 14	15	16 24h	17 48h	18 72h	19 96h	20 120h				
Urine PK			X	X (Day 2, end of 24hr collection from Day 1)	X	X (Day 9, end of 24hr collection from Day 8)	X	X (Day 16, end of 24hr collection from Day 15)						Hours (h) relate to PK sampling post last dose		

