2.2. Study Objective(s) and Estimand(s) / Endpoint(s)

[figure not shown]
Objectives	Endpoints
Primary Objectives	Primary Endpoints

 • To investigate the safety and tolerability of VH3739937 following single and repeated daily and weekly oral administration in healthy participants (Part 1 & 2) • To assess the safety and tolerability of VH3739937 following single oral administration in healthy participants under fasted or fed (moderate calorie and fat) conditions (Part 3) • To evaluate the relative bioavailability (RBA) of VH3739937 powder in bottle (PiB) versus VH3739937 tablet and the effect of food on the PK of VH3739937 tablets and VH3739937 PiB (Part 3) 	
VH3739937 safety parameters:
 
 • Adverse events; post baseline values and changes over time of clinical laboratory evaluations (haematology, clinical chemistry, urinalysis), vital signs, and ECG parameters from pre-dose values (Part 1, 2, and 3) • Derived PK parameters for VH3739937, as data permits: Part 3 (single dose): $AUC_{(0-24)}$, $AUC_{(0-\infty)}$, C_{max},
Secondary Objectives	Secondary Endpoints

 • To describe the PK profile of VH3739937 following single (Part 1 and 3) and repeated daily and weekly oral administration in healthy participants (Part 2), as data permits 	
Derived PK parameters for VH3739937, as data permits:
 
 • Part 1 (single dose): $AUC_{(0-24)}$, $AUC_{(0-t)}$, $AUC_{(0-\infty)}$, C_{max}, C_{24}, t_{max}, t_{lag}, $t_{1/2}$, C_{last}, t_{last}, CL/F • Part 2 (repeated once daily [QD] dose):

Objectives	Endpoints
	
 ○ Day 1: $AUC_{(0-24)}$, C_{max}, C_{24}, t_{max}, t_{lag} ○ Day 14 (Cohorts 3 and 4): $AUC_{(0-\tau)}$, C_{max}, $C\tau$, t_{max}, $t_{1/2}$, and CL/F ○ Day 14 (Cohort 5): $AUC_{(0-\tau)}$, C_{max}, $C\tau$, t_{max} ○ Day 18 (Cohort 5): $AUC_{(0-\tau)}$, C_{max}, $C\tau$, t_{max}, $t_{1/2}$, and CL/F ● Part 2 (repeated once weekly [QW] dose, as data permits: 
 ○ Day 1 (Cohort 6): $AUC_{(0-168)}$, C_{max}, C_{168}, t_{max}, t_{lag} ○ Day 8 (Cohort 6): $AUC_{(0-168)}$, C_{max}, C_{168}, t_{max} ○ Day 15 (Cohort 6): $AUC_{(0-t)}$, C_{max}, $C\tau$, t_{max}, $t_{1/2}$, and CL/F ● Part 3 (single dose): $AUC_{(0-24)}$, $AUC_{(0-\infty)}$, C_{max}, C_{24}, t_{max}, t_{lag}, $t_{1/2}$, C_{last}, t_{last}, CL/F

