8.1.1.2. Derived Pharmacokinetic Parameters

Pharmacokinetic parameters will be calculated by standard non-compartmental analysis according to current working practices and using the currently supported version of WinNonlin. All calculations of non-compartmental parameters will be based on actual sampling times. Pharmacokinetic parameters listed will be determined from the plasma concentration-time data, as data permits.

Parameter	Parameter Description
AUC(0-inf)	Area under the concentration-time curve extrapolated to infinity will be calculated as: AUC = AUC(0-t) + C(t) / lambda_z
AUC(0-t)	Area under the concentration-time curve from time zero to the time of the last quantifiable concentration (C(t)) will be calculated using the linear trapezoidal rule for each incremental trapezoid and the log trapezoidal rule for each decremental trapezoid.
AUC(0-24)	Area under the plasma concentration time curve from zero to 24 hrs
AUC(0-168)	Area under the plasma concentration time curve from zero to 168 hrs
AUC(0- τ)	Area under the curve (Area under the plasma drug concentration-time curve from pre-dose to the end of the dosing interval at steady state)
%AUCex	The percentage of AUC (0-inf) obtained by extrapolation (%AUCex) will be calculated as: [AUC(0-inf) – AUC(0-t)] / AUC(0-inf) x 100
C _{max}	Maximum observed concentration, determined directly from the concentration-time data.
C ₂₄	Concentration at 24 hours post-dose
C ₁₆₈	Concentration at 168 hours post-dose
C _{last}	Last quantifiable concentration

Parameter	Parameter Description
$C\tau$	Pre-dose (trough) concentration at the end of the dosing interval
t_{max}	Time to reach C_{max} , determined directly from the concentration-time data.
$t_{1/2}$	Apparent terminal half-life will be calculated as: $t_{1/2} = \ln 2 / \lambda_{z}$
t_{lag}	Absorption lag time
t_{last}	Time of last quantifiable concentration
CL/F	Apparent oral clearance

NOTES:

- Additional parameters may be included as required.

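### Cohort 5: the schedule places the 24-hour sample for the Day 14 dose post-dose on Day 15, a dosing day, although the analyses use it as a pre-dose trough

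*Protocol*

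**What the plan says.** Protocol section 1.2, Table 4 (Cohort 5) gives the dosing as "Once-daily oral dose from Day 1 to Day 18", so Day 15 is a dosing day. The plasma PK note in that table makes three statements:

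- After the first dose, the "24 hour post Day 1 dose collection will be pre-dose on Day 2".
- After the Day 14 dose, "the 24 hour post Day 14 dose collection will be post-dose on Day 15".
- "At all other timepoints on dosing days, samples will be drawn pre-dose prior to dose administration".

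No separate pre-dose plasma sample on Day 15 is named. The metabolite note in the same table takes its timepoints from the plasma PK samples, Day 15 included.

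Table 3 (Cohorts 3 and 4) has the parallel clause: "the 24 hour post Day 14 dose collection will be post dose on Day 15 (24 hours after the last dose"). Dosing there ends on Day 14.

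The analyses treat the Day 15 value as a trough:

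- The steady-state endpoint for Cohort 5 in protocol section 3 is the set of pre-dose concentrations on Days 2 to 18.
- SAP section 2.2 has an entry for "Day 14 (Cohort 5") that includes AUC(0-τ) and Cτ. SAP 8.1.2 repeats it.
- SAP 8.1.1.2 defines Cτ as "Pre-dose (trough) concentration at the end of the dosing interval".
- SAP 8.1.5.1.3 regresses the Day 2 to Day 18 pre-dose values plus the Day 19 24-hour value. The footnote to Table 4.6 in SAP 13.10.6 lists Day 15 as a trough day for Cohort 5.

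**The concern.** The Day 1 and Day 14 samples are in the same position: each falls 24 hours after a dose, when the next dose is due. One is placed before that next dose and the other after it. Only the Day 1 placement yields a trough.

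If a site follows Table 4 as written, the Day 14 Cτ for Cohort 5 includes drug from the Day 15 dose, and one point of the steady-state series is not a trough. A draw made as scheduled would not be a deviation, so deviation review need not catch it. Using actual sampling times in the non-compartmental analysis (SAP 8.1.1.2) does not protect the regression, because SAP 13.5.2 uses planned time for statistical analyses unless stated otherwise.

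The SAP looks for the onset of steady state by dropping early days one at a time and re-estimating the slope. A high value at the start of a short window pulls that slope down and could make steady state look reached earlier than it was.

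**Working it through.** The plan gives no figure for this effect, so the check is its size.

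**Inputs.** Half-life about 90 h (protocol 4.1). Median Cτ 1.57 and Cmax 1.72 µg/mL at 100 mg once daily (protocol Table 11). Sampling days from Table 4: 2, 3, 4, 6, 8, 10, 12, 14 to 19. The absorption rate ka is not given; I assume 0.1 to 1.0 per hour. The documents also give no time limit for the post-dose draw; 15 minutes is my assumption.

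**Input check.** Accumulation = 1/(1 − 2^(−24/90)) = 5.9, which agrees with the protocol's figure of about 6-fold for daily dosing.

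**Inflation of the Day 15 value** relative to the pre-dose value (one compartment, first-order absorption, 14 prior doses):

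| ka (per h) | 15 min after dose | 1 h | 4 h |
|---|---|---|---|
| 0.1 | 0.4% | 1.4% | 4.4% |
| 0.2 | 0.8% | 3.1% | 8.5% |
| 0.5 | 2.3% | 7.7% | 15.3% |
| 1.0 | 4.6% | 12.9% | 17.9% |

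Table 11 gives a peak-to-trough ratio of 1.72/1.57 = 1.096, so on the plan's own projection a draw near the peak overstates the median trough by about 10%. Of the assumed rates, 0.2 per hour comes closest to that ratio (10.0% at 6 h). The larger entries for 0.5 and 1.0 exceed what Table 11 projects.

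**Steady-state slope.** The trough on Day d, as a fraction of steady state, is f(d) = 1 − 0.5^(24(d−1)/90). For Days 15 to 19 this gives 0.925, 0.937, 0.948, 0.957 and 0.964. The true rise from Day 15 to Day 16 is 0.9375/0.9248 − 1 = 1.4%. Least-squares slopes per day:

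| Window | True | Day 15 +0.4% | Day 15 +4.6% | Day 15 +9.6% |
|---|---|---|---|---|
| Days 2-19 | 0.0428 | 0.0429 | 0.0432 | 0.0436 |
| Days 10-19 | 0.0166 | 0.0166 | 0.0165 | 0.0164 |
| Days 12-19 | 0.0133 | 0.0132 | 0.0123 | 0.0111 |
| Days 14-19 | 0.0108 | 0.0105 | 0.0072 | 0.0033 |
| Days 15-19 | 0.0098 | 0.0091 | 0.0013 | −0.0079 |
| Days 16-19 | 0.0089 | 0.0089 | 0.0089 | 0.0089 |

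In the Days 15-19 window, inflating Day 15 by a fraction p lowers the slope by 0.2 × 0.925 × p. The sign changes only when p exceeds 0.0098/(0.2 × 0.925) = 5.3%. No assumed ka reaches that at 15 minutes.

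**AUC(0-24) on Day 14.** With a nearly flat profile, a 10% error in the 24 h value acts only through the 16-24 h trapezoid: 0.5 × 8 × 0.10/24 = 1.7%. A 4.6% error gives 0.8%.

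**The case against.** **Intent.** The text can be read as meaning only 24 hours after the Day 14 dose. Other entries point to a pre-dose draw: the steady-state endpoint is pre-dose, and the Day 15 Holter and urine entries close the 24-hour collection begun on Day 14. The sentence covering all other timepoints does not prove the opposite, since one of the timepoints it sets aside, Day 2, is itself pre-dose. This stands as evidence of intent, and it means the sample could be, not certainly would be, drawn after the dose. It does not remove the conflict: the Day 2 sample is equally 24 hours after a dose, yet the same note calls it pre-dose.

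**Size.** A reader might infer that the trough will be overstated by about 10% and the steady-state slope reversed. The documents do not support that. The sample is labelled as the 24-hour collection, which falls at the Day 15 dose time. A draw near the peak would come hours later and miss that label. A sign change is also confined to the Days 15-19 window. The slopes above are free of noise: with 7 active participants and an assumed residual CV of 12.5%, the 90% CI half-width there is about 0.023 per day, wider than the worst-case shift of 0.018. At 5% CV it is about 0.009, narrower than that shift.

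**Use.** No principal Cohort 5 result depends on this sample. The protocol's repeat-dose profile, the accumulation ratio and the PK stopping rule all use Day 18. The Day 14 parameters for Cohort 5 are listed only in the SAP. This stands and limits the point.

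**Table 5.** A reader might infer a similar loss in Cohort 6, where the note reads "24 h post day 1 dose collection on Days 2, 9 and 15 will be taken at post-dose collection timepoint" although Day 15 is the third dosing day. Nothing is lost: the same note lists Day 16 among the sampled days, and the table marks it in the 24 h column. That is a clerical slip and not part of this point.

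**Conclusion.** The inconsistency is real: Table 4 as written places a value that is analysed as a trough after the next dose. The exposed results are the Cohort 5 Day 14 Cτ, to a small degree the Day 14 AUC(0-τ), the steady-state windows that include Day 15, and the Day 15 metabolite sample.

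The probable bias is modest, about 0.4% to 4.6% under the assumed absorption rates and a 15-minute delay. About 10% is a worst case at odds with the sample's own 24-hour label. Only windows starting near Day 15 move materially, and the Days 15-19 slope turns negative only with inflation above 5.3%, which needs a draw well after dosing. The final Days 16-19 window, the Day 18 profile, the Day 18/Day 1 accumulation ratios and the stopping rule are unaffected. The point merits correction because the remedy is nearly free, not because a main conclusion is at risk.

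**What to change.** In the Table 4 plasma PK note, change the timing of the 24-hour sample for the Day 14 dose from post-dose to pre-dose on Day 15, matching the treatment of Day 2. State that the Day 15 metabolite sample follows the same timing.

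In the SAP, add that any Cohort 5 Day 15 sample actually drawn after the Day 15 dose is excluded from Cτ and from the steady-state regression, judged by the recorded sample and dose times.

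The cost is a one-word correction, a clarifying phrase and one SAP sentence, with no extra blood draws or visits.

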2. INTRODUCTION

2.1. Study Rationale

The inhibition of maturation and release of human immunodeficiency virus-1 (HIV-1) is a novel target for drug development, distinct from viral protease, reverse transcriptase and integrase. There are no maturation inhibitors (MI) approved for the treatment of HIV infection. VH3739937 is a MI that displays *in vitro* evidence of low nanomolar potency against multiple HIV-1 Gag polymorphisms and a broad spectrum covering multiple HIV-1 subtypes, supporting compound development. This is a double-blind (sponsor-unblinded), randomised, placebo-controlled, first-time-in-human (FTIH) study in a combined single- and multiple-dose protocol to investigate the safety, tolerability and PK of VH3739937 in healthy participants. This study is designed in three parts: i) to gain information on the safety, tolerability, and pharmacokinetic properties of VH3739937 when administered as powder-in-a-bottle (PiB); ii) the relative bioavailability (RBA) of the GSK3739937 PiB and GSK3739937 Tablet and; iii) to evaluate the safety, tolerability and pharmacokinetic (PK) parameters of the tablet formulation when administered under fasting and fed conditions. This study will enable further clinical development of VH3739937, including a Phase IIA Proof of Concept (PoC) study in HIV-infected patients, a First-Time-in-Human study of the long acting formulation of VH3739937, as well as supporting the future studies of parenteral administration (subcutaneous and intramuscular routes) of a long acting formulation of VH3739937.

2.2. Background

It is estimated that approximately 38 million people are currently living with HIV/Acquired Immunodeficiency Syndrome (AIDS) and that the worldwide epidemic continues to grow at a rate of 1.7 million new infections and cause 770,000 deaths per year [Fact sheet, 2019]. Chronic HIV infection in adults continues to be characterized by increased development of resistant virus, increasing transmission of resistant virus and issues associated with long term toxicity of anti-retroviral therapy (ART). The current paradigm in the treatment of HIV involves life-long therapy with multiple antiretrovirals. This dependency on medical therapy requires a need for continuous improvement on the durability, tolerability and convenience of all antiretroviral classes.

Chronic exposure to combination anti-retroviral therapy (cART) has identified anti-retroviral (ARV)-associated long-term toxicities (e.g. central nervous system (CNS) or cardiovascular (CV)/metabolic effects, renal disease, etc.), creating a need to address and prevent these co-morbidities. Regimens which avoid particular classes of agents may help avoid or manage comorbidities among people living with HIV (PLHIV) and the use of 2 drug regimens have the potential to reduce long term toxicities by reducing ARV exposure. Treatment failure remains a continuing concern in clinical care due to the presence and emergence of resistant strains and tolerability issues. In addition, managing an ageing population of PLHIV with an increasing prevalence of comorbidities and polypharmacy requires ARVs with the potential for fewer drug-drug interactions.

VH3739937, an HIV-1 maturation inhibitor (MI) has a novel mechanisms of action (MoA) and has the potential to meet these required characteristics for future therapy.

There is considerable interest in long acting antiretroviral therapy which allow less than daily dosing among PLHIV. Long acting (LA) regimens offer potential advantages over daily oral regimens including less frequent dosing, improved adherence, treatment satisfaction and outcomes.

The inhibition of maturation and release of human immunodeficiency virus-1 (HIV-1) is a novel target for drug development, distinct from viral protease, reverse transcriptase or integrase. There are currently no MIs approved for the treatment of HIV infection.

VH3739937 is a MI that displays *in vitro* evidence of low nanomolar potency against multiple HIV-1 Gag polymorphisms and a broad spectrum covering multiple HIV-1 subtypes, supporting compound development and has the potential to be developed as a long acting formulation as well as an oral formulation. It is anticipated the oral version will be used as an oral lead in to establish short term safety and tolerability prior to LA administration or to bridge periods where LA dosing is not possible. The oral version of VH3739937 will support the undertaking of the phase 2a POC study and drug-drug interaction studies.

VH3739937 is a next-generation HIV MI with a similar chemical structure and profile to GSK3640254 which is being developed as an oral ARV. Both MIs have improved profile over prior developmental MIs as they (1) exhibit significantly improved pan-genotypic coverage and potency against polymorphic variants; (2) *in vitro* data suggest that both MIs exhibit a higher barrier to emergence of resistant viruses (except for A364V); (3) both MIs have improved potency *in vitro* toward all HIV-1 subtypes; and (4) it has a projected lower once-daily (QD) human dose. Summaries of the pre-clinical studies are included in the Clinical Investigator's Brochure (CIB) [GlaxoSmithKline Document Number [2019N421306_00](#)].

2.2.1. Background Key Safety and PK data with Prior Maturation Inhibitors (GSK3532795 and GSK3640254)

Bristol-Myers Squibb (BMS), and later ViiV Healthcare (VH), developed an HIV-1 MI (GSK3532795), which was studied through Phase 2b studies in both treatment-naïve (AI468038) and experienced (AI468048) HIV-1 infected adults. In study AI468038, a greater number of participants who received GSK3532795 experienced gastrointestinal (GI) intolerance (specifically G1-2 diarrhoea and abdominal pain). A detailed examination of all GI AEs (regardless of Grade/Relationship) revealed a relationship with dose [GlaxoSmithKline Document Number [2016N302783_00](#)]. Ultimately, the rate of GI intolerance in the GSK3532795 dose groups in the Phase 2b study AI468038, helped lead to VH's decision to end all clinical trials and not progress to Phase 3 studies.

GI AEs were also previously observed in healthy participants in Phase 1 studies with varying doses, durations, and formulations of GSK3532795. First, in AI468049, the rates of GI AEs ranged from 33-67% across cohorts (single oral doses of GSK3532795 60 mg – 180 mg with food) [GlaxoSmithKline Document Number [2016N297636_00](#)]. Second, in AI468063, 65% of participants receiving GSK3532795 180 mg QD with food

developed diarrhoea [GlaxoSmithKline Document Number [2017N319618_00](#)]. Finally, in AI468052, 29% of participants who received GSK3532795 180 mg once daily (QD) with food developed GI AEs. In all three studies, the most common GI AEs were abdominal pain and diarrhoea.

Aside from mild-moderate GI intolerance, two SAEs occurred in phase I study AI468044 in healthy participants receiving supra-therapeutic doses of GSK3532795: one healthy participant had acute psychosis and another had suicidal ideation/homicidal ideation as diagnosed by a psychiatrist. These two participants received GSK3532795 240 mg twice daily (BID) and 240 mg QD for 3 days with food, respectively. These events were not observed in any other clinical study with GSK3532795. The most frequent neuropsychiatric AEs in studies with GSK3532795 were headache, dizziness and sleep abnormalities (e.g. insomnia, abnormal dreams) [GlaxoSmithKline Document Number [2017N332341_00](#)].

GSK3640254, was evaluated in a First time in human study (207187) and in a Phase 2a proof of concept study in HIV-1 infected, treatment-naïve patients. Study 207187 was carried out in two parts (Part 1 and Part 2). Participants in Part 1 received single ascending doses of GSK3640254 (1-700 mg) and participants in Part 2 received repeated daily doses of GSK3640254 at different concentrations (50-320 mg)

GSK3640254 did not show any major tolerability findings (including AEs, vital signs, ECG findings, or laboratory values) when given to healthy males in single doses (up to 700 mg) or daily doses (up to 320 mg QD for 14 days), supporting further clinical development of GSK3640254. Three participants from Part 1 and one participant from Part 2 of the study were withdrawn due to adverse events.

GI related AEs were reported in 6 of 16 participants from Part 1 and 13 of 56 participants from Part 2 of the study. All these events were mild in intensity. No dose/AE relationship and no major GI tolerability issues were observed in this study.

Psychiatric AEs were reported in 2 of 16 participants from Part 1 and in 6 of 56 participants from Part 2 of the study. All these events were mild (except 1 event of depression in Part 1 that was moderate in intensity in a participant with history of family stressors prior to study entry) and none were considered related to the study treatment.

Neurologic AE of headache was reported in 6 participants from Part 1 and in 15 participants from Part 2. There were no major GSK3640254 related neuro/psychiatric events observed. None of these events (except 1 in Part 2) were considered related to the study treatment.

Skin tissue disorders AEs, contact dermatitis due to ECG leads were reported in 5 out of 16 participants in Part 1. In Part 2, 14 out of 56 participants reported skin related AEs, contact dermatitis due to ECG leads n=8, dry skin, eczema nummular, miliaria, pruritus rash and rash maculo-papular. All events were mild in intensity and none was considered related to study treatment. One event lead to study discontinuation (rash maculo-papular).

Though there were a number of participants with ECG abnormalities in both parts of the study, none of these findings were considered clinically significant. There were no

clinically significant arrhythmias reported in either Part 1 or Part 2 of the study. No participants had a QT interval corrected for heart rate according to Fridericia's formula (QTcF) value of >500 msec or an increase from baseline >60 msec. A cardiodynamic evaluation of the multiple ascending dose portion of Study 207187 was undertaken based upon concentration vs change from pre-dose QT interval corrected (QTc) using 12-lead Holter ECGs an analysis by iCardiac/eRT. This indicated a weak relationship between QT prolongation and GSK3640254 plasma concentrations and indicated that an effect on QTcF can be excluded up to GSK3640254 plasma concentration of ~2000 ng/mL [GlaxoSmithKline Document Number [2018N392814_01](#)].

To characterize the population pharmacokinetics of VH3739937 and identify important determinants of variability, a population model was conducted as an alternate analysis approach to characterize the pharmacokinetics and the simulation was implemented to predicted the higher single dose and multiple dose cohort PK profile based on the model. The PK of VH3739937 following oral administration was adequately characterized by a linear one-compartment model with first-order absorption and first-order elimination, and with a dose factor and inter-individual variability on CL/F and on the magnitude of proportional residual error. The simulations for higher single dose 640 and 800 mg, multiple daily dose 50 and 100 mg and the multiple weekly dose 500 mg were conducted to predict the PK profile to obtain the Cmax and AUC for safety cover. More detailed information can be found in the Investigator's Brochure Supplement [GlaxoSmithKline Document Number [2021 RPS_CLIN_004025](#)].

